The actual dates and times of sample collection must be recorded in the eCRF. When occurring on the same day, safety and biomarker blood samples may be collected at the same time as PK sampling to minimize the number of venipunctures. A predose PK sample is defined as one collected within 0.5 hour (≤ 30 minutes) prior to the next dose. Additional PK samples may also be collected on an ad hoc basis as a safety assessment in the event that a safety event arises for which an understanding of drug exposure is clinically important, at the discretion of the investigator or at the request of the sponsor.

See [Attachment 8](#) for details on PK sampling and collection of food intake information.

- x. Prestudy therapies administered up to 7 days before the first dose of study drug must be recorded at screening. Concomitant therapies must be recorded throughout the study beginning with the start of the first dose of study drug up to the Day 28 visit (± 2 days). During hospitalization, concomitant medication will be recorded by the site staff in the eCRF. Upon discharge, subjects will be required to document use of concomitant medication in the electronic device in a medication log, which will serve as basis for recording the concomitant medication in the eCRF by the site staff.
- y. All AEs and SAEs will be collected continuously from signing of the ICF onwards until the last follow-up visit (EoS visit). Any clinically significant abnormalities persisting at the EoS/early withdrawal will be followed by the investigator until resolution or until a clinically stable endpoint is reached.

- z. The ordinal scale will be assessed on the day of the last dose (Day 5/6 [depending on the timing of the LD administration]). In case the subject is discharged before Day 5/6, the subject should be contacted to ask if the subject has returned to usual activities.

ABBREVIATIONS

ADL	Activities of Daily Living
AE	adverse event
ALT	alanine aminotransferase
AST	aspartate aminotransferase
AUC	area under the curve
AUC _{0-inf}	area under the concentration-time curve from time zero extrapolated to infinite time
AUC _{0-last}	area under the concentration-time curve from time zero to the time of the last quantifiable concentration
AUC _{0-xh}	area under the concentration-time curve from time 0 to x hours after dosing
BCRP	breast cancer resistance protein
BFU-E	burst forming unit-erythroid
CFU-GM	colony forming unit-granulocyte monocyte

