The ordinal scale consists of 6 categories that are exhaustive, mutually exclusive, and ordered (Table 6). For all subjects, the category at Day 5/6 (depending on the timing of the LD administration) will be established as the worst category on that day. For example, if a subject is discharged on Day 6, the category will be non-ICU and no supplemental oxygen (if there was no supplemental oxygen given on that day). The analysis will be performed using a proportional odds model, modeling the common odds ratio of the improvement on the ordinal scale of active treatment versus control. Baseline covariates that are predictive of the ordinal scale may be added to the model to increase the model fit. In case of missing data (>10%), a multiple imputation method under the missing-at-random assumption will be employed. Details will be provided in the SAP.

Table 6: Ordinal Scale on Day 5/6 (Depending on the Timing of the LD Administration)

Outcome
Death
Admitted to ICU
Non-ICU hospitalization requiring supplemental oxygen
Non-ICU hospitalization not requiring supplemental oxygen
Not hospitalized, unable to resume normal activities
Not hospitalized, resumption of normal activities

ICU = Intensive Care Unit

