Time to normal temperature (hours) [Time-to event]	
Minimum[date and time of Time of return to pre-RSV disease level temperature, date and time of last measurement] - date and time of first dose of study drug)/3600[†], rounded to one decimal
 
If none of the values are abnormal for the subject, this value will be set at time 0.
 
Subjects with an abnormal value at the last assessment will be censored. Subjects for which this last assessment is the baseline assessment will be censored at time 0.

Time point of return to pre-RSV functional status (KATZ ADL score)	
The first time point where the KATZ ADL score is equal or higher than the pre-RSV disease KATZ ADL score and no lower scores are measured after this time point.
 
Functional status is the total points on the KATZ Index of Independence in Activities of Daily Living (KATZ ADL score)

Time to return to pre-RSV functional status (KATZ ADL score) (days) [Time-to-event]	
minimum[date and time of time of return to pre-RSV functional status, date and time of last measurement] - date and time of first dose of study drug)/3600, rounded to one decimal
 
If the KATZ ADL score is never lower than the pre-RSV score, this value will be set at time 0.
 
Subjects with a functional status lower than the pre-RSV disease functional status at the last KATZ ADL assessment will be censored. Subjects for which this last assessment is the baseline assessment will be censored at time 0.

Ordinal scale score	
The value as collected in the eCRF on the day of last dose (Day 5/6 depending on timing of LD) will be used as score on the day of last dose. Only in case of a missing score, the score will be calculated based on the available information in the eCRF.
 
The 6 categories to be considered are:

	
 • Death • Admitted to ICU • Non-ICU hospitalization requiring supplemental oxygen • Non-ICU hospitalization not requiring supplemental oxygen • Not hospitalized, unable to resume normal activities • Not hospitalized, resumption of normal activities 
Subjects will receive a score ranging from 1 (=subject died on or before of their day of last dosing) to 6 (=subject was not-hospitalized, resumption of normal activity) depending on his status on day of last dosing
 
For days 3 to 14, the ordinal scale will be calculated on each day, using the algorithm described above.

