The time to return to pre-RSV disease level (hours) for RR, SpO₂ and body temperature will be analyzed using the same approach as for the Time to SpO₂ ≥ 93% (hours) on room air.

Time to return to pre-RSV functional status (KATZ ADL score) (days)

Time to return to pre-RSV functional status (KATZ ADL score) (days) will be analyzed using the same approach as for the Time to SpO₂ ≥ 93% (hours) on room air.

Time to clinical stability (hours)

The time to clinical stability (hours) will be analyzed using the same approach as for the Time to SpO₂ ≥ 93% (hours) on room air.

Ordinal scale

The number and percentage of subjects will be summarized for the ordinal scale by treatment group at the end of the treatment period (Day 5/6).

The analysis will be performed using a proportional odds model, modeling the common odds ratio of the improvement on the ordinal scale of each active treatment versus control. Age category (≥50 to <65 years and ≥65 years) and region (Japan, non-Japan) will be added to the model as fixed factors. For each of the 5 possible cut-points the odds ratio will also be presented (comparing active versus placebo) to verify the common odds assumption.

For the ordinal scale also descriptive statistics will be computed for each post-baseline day (days 3 to 14 and day of last dose). Here missing data will be imputed using the LOCF approach.

All-cause mortality

The number and percentage of subjects who died will be summarized and compared between treatment groups using the logistic regression approach described before.

Note that this analysis will only be performed if any deaths did occur.

Viral load over time

Descriptive statistics and mean (SE) plots will be shown for the log₁₀ values of RSV RNA viral load and the changes from baseline calculated in log₁₀(copies/ml) by treatment group.

Peak viral load/Rate of decline:

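### The SAP ties the ordinal score, including Death, to the day of last dosing; for subjects who stop early this can depart from the Day 5/6 that the protocol sets for everyone

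*SAP*

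**What the plan says.** **Protocol.** Section 11.3 states, for all subjects, that "the category at Day 5/6 (depending on the timing of the LD administration) will be established as the worst category on that day". Table 6 in that section carries the same day in its title. Footnote z of the Time and Events Schedule is looser: "The ordinal scale will be assessed on the day of the last dose", which it then equates with Day 5/6 according to loading-dose (LD) timing.

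**SAP, section 4.2.4.1, Table 1.** The row for the ordinal score starts from "The value as collected in the eCRF on the day of last dose (Day 5/6 depending on timing of LD"). It adds: "Only in case of a missing score, the score will be calculated based on the available information in the eCRF". Score 1 (Death) applies when the "subject died on or before of their day of last dosing", and the full range of scores is assigned "depending on his status on day of last dosing". The row ends: "For days 3 to 14, the ordinal scale will be calculated on each day".

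**SAP, section 4.2.4.2.** The categories are summarised "at the end of the treatment period (Day 5/6") and analysed with a proportional odds model. The daily scores are described only, and the day of last dose is listed there as a time point beside Days 3 to 14.

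Neither document says which day is scored for a subject whose dosing ends before Day 5/6.

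**The concern.** Subjects who stop early belong in this analysis. Protocol section 10.2 keeps them in the study, and the ITT-i set in SAP section 2.3 needs only one dose and central confirmation of RSV. If last dosing is programmed as each subject's actual last intake, two things follow. A death between the last dose and Day 5/6 is not scored as Death. Survivors who stopped early are scored at an earlier point in the illness than their comparators.

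The scoring day would then be a post-randomisation variable. Stopping is mandatory under several laboratory criteria (protocol sections 9.7.1 and 10.2) and for some rashes (Attachment 7). Protocol section 9.9.4 names haematopoietic toxicity as a potential risk of the drug. Early stopping could therefore differ by arm and enter the common odds ratio.

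Three features make the actual-day reading realistic in practice:

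- SAP sections 2.1 and 4.1.4 define the treatment phase and treatment duration from actual last intake.
- Footnote a of the Time and Events Schedule re-times the follow-up visits of discontinued subjects from the last dose given, so a site could apply footnote z in the same way.
- Table 1 gives a collected eCRF value precedence, so a value entered on an early last-dose day would stand even if later data show ICU admission or death by Day 5/6.

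**Working it through.** The documents give no power, alpha or event-rate figure for this endpoint, so there is no plan figure to reproduce. The check is of the text, with a dose count and an illustration.

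**1. When is the scheduled last dose?** Inputs from protocol section 6: one loading dose plus nine maintenance doses, at most two doses per calendar day.

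- Two doses on Day 1: 2 × 5 = 10, so dose 10 falls on Day 5.
- One dose on Day 1: 1 + 2 × 4 = 9 by the end of Day 5, so dose 10 falls on Day 6.

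Day 5/6 by LD timing is therefore the scheduled last-dose day of a completer. For completers the SAP and protocol definitions coincide.

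**2. Where do the readings part?**

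| Subject | Score by actual last-dose day | Score on scheduled Day 5/6 |
|---|---|---|
| Completes 10 doses | Status on Day 5 or 6 | Same |
| Last dose Day 3, dies Day 4 | Day 3 status: 2 or better, because Day 4 is after Day 3 | 1 (Death) |
| Last dose Day 3 on oxygen in a ward; by Day 4 home, not yet back to normal activities, and unchanged on Day 5/6 | 3 | 5 |

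The second row moves a death to a better category. The third moves a recovering survivor to a worse one. The net direction of any bias in the odds ratio is not fixed.

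**3. How many subjects?** Planned size is about 30 per arm (protocol section 3.1). The early-stopping rate is not in the documents, so these rates are assumptions:

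- 5%: 30 × 0.05 = 1.5 per arm
- 10%: 30 × 0.10 = 3 per arm
- 20%: 30 × 0.20 = 6 per arm

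One reclassified death is 1/30 = 3.3 percentage points of an arm.

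**4. Extended dosing.** The Time and Events Schedule allows up to 19 maintenance doses, that is 20 doses in all. The count in step 1 then puts the last dose on Day 10 (two doses on Day 1) or Day 11 (one dose). The day of last dose and Day 5/6 would no longer be the same day even for completers. SAP sections 4.2 and 4.1.3 adapt the primary endpoint and the compliance calculation to an extension; the ordinal-score row does not.

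**The case against.** The strongest reply is that the documents, read together, already mean the scheduled day. Table 1 never says actual. Its bracket depends on LD timing, which fixes the scheduled day of dose 10 and has nothing to do with discontinuation. Section 4.2.4.2 names Day 5/6 as the analysis time point. The words on or before also fit a scheduled day better: nobody can die before the day of their own actual last dose, so on the actual-day reading half of that phrase is empty. Footnote z makes the same equation and treats Day 5/6 as the reference for subjects discharged earlier. SAP section 1 says the plan is to be read with the protocol. Listing the day of last dose beside Days 3 to 14 proves little, since a pooled Day 5/6 time point needs its own label.

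All of that stands, and it limits the finding. A reader might infer that the SAP definitely scores each subject on the actual last-dose day and so records deaths as better outcomes. The text does not establish that. Nor does it support an example with scoring on Day 2: the schedule places the assessment in the Days 3 to 6 column, and the daily derivation starts at Day 3. It is likewise an inference that the scoring day would move under extended dosing; on that the documents are silent.

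The reply does not remove the gap. The possessive wording about last dosing and the precedence of the eCRF value are in the operative definition, and no sentence tells a programmer or a site what to do for an early stopper. The Days 3 to 14 scores would show a misclassified death but are descriptive, so they would not correct the odds ratio.

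**Conclusion.** The concern holds as an inconsistency between SAP Table 1 and protocol section 11.3 that matters only for ITT-i subjects whose dosing ends before Day 5/6. Applied literally to them, the SAP wording scores an earlier day and omits a death between the last dose and Day 5/6.

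The size is unknown from the documents. The figures of about 1.5 to 6 of 30 per arm rest on assumed stopping rates of 5% to 20% and count everyone scored on a different day, not deaths. No rate of early stopping followed by death before Day 5/6 is given, and no size or direction of bias in the common odds ratio can be claimed.

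The stakes are moderate. The endpoint is secondary, plays no part in the sample-size calculation, and leaves the primary analysis untouched. Any death is also counted under all-cause mortality. It is, however, one of the selected secondary endpoints given supportive ITT and per-protocol analyses (SAP section 2.3), and the ambiguity should be closed before programming and unblinding.

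**What to change.** Amend the ordinal-score row of SAP Table 1 to say that:

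- every ITT-i subject is scored on the scheduled Day 5 or Day 6 set by LD timing, whatever the actual last dose;
- any death on or before that day is scored 1;
- this derivation overrides an eCRF value recorded on an earlier day.

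Align footnote z of the protocol schedule with section 11.3. Because section 11.3 and Table 6 name only Day 5/6, state that this day also applies if dosing is extended, or reconcile the passages.

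The cost is wording in the SAP and one protocol footnote. No new assessment is needed: daily scores for Days 3 to 14 are already to be derived, and subjects who stop treatment are asked to continue with study assessments. A survivor who leaves the study before Day 5/6 would still have missing data, to be handled under the existing missing-data provisions.

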4.2.3. Primary Efficacy Endpoint

4.2.3.1. Definition

The primary estimates of the AUC will be derived from a mixed model (see section 4.2.3.2 for the detailed specification). No imputations of missing data from nasal swabs post-baseline will be done in this model, as this mixed model would allow to make inferences under the *missing at random* assumption.

Note that for the primary endpoint the following rules apply:

- Only values as provided by the central lab will be used.
- Baseline (Day 1) is defined as the last measurement before first intake. In case a result is available that is no later than 1 hour after treatment initiation this may be used but only if no pre-treatment observation is available.
- If for the baseline assessment the central laboratory value is missing, the value that will be imputed is based on the average value as based on the analysis population (ITT-i, ITT or PP population).
- For all post-baseline days the RSV RNA viral load result of the swab that was performed at that day will be used, counting from the Day of first treatment which is defined as Day 1.
- In case multiple nasal swabs were taken on a single day the average on the log scale will be used as the value for that subject.

As a sensitivity analysis, descriptive statistics will be provided for the viral load AUC calculated by the trapezoidal summation rule, based on planned days of sampling (Baseline visit up till/including Day 7 visit, or up to 11 days if the dose duration is extended to up to 10 days), including the timepoints with (imputed) values available:

$$AUC_{0-7 \text{ days}} = \frac{1}{2} \sum_{i=1}^n (y_i + y_{i-1}) \times (t_i - t_{i-1})$$

where $i=1,2,3,\dots,n$ are the time points when post baseline samples are collected, y_i is the log 10 viral load at the time and t_i is the time in hours post baseline. y_0 is the baseline log 10 viral load. t_0 is time 0.

The following additional rules, on top of the rules of the primary analysis, will be applied to deal with missing values post-baseline before calculating the Viral load AUC:

- Missing value between baseline and day 7 will be imputed by intrapolation.
- If the last observations are missing, the last available observation will be carried forward. Unscheduled assessments will be included and will be eligible for carrying forward.

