4.2.4. Secondary Efficacy Endpoints

4.2.4.1. Definition

Formulae to be used for derived variables, including data conversions, are provided in [Table 1](#). In the derivation of durations described below, no imputation of the start and/or end date/time will be performed.

Table 1. Calculations and Conversion Formulae

Measurement	Formula
Length of hospital stay (hours) [Time-to event]	(Date and time of event or censoring - date and time of first dose of study drug)/3600, rounded to one decimal
Time to readiness for discharge (hours) [Time-to-event]	Subjects who complete or withdraw from the study prior to the event will be censored at the date of completion or withdrawal. If the time is not available they will be censored at 12:00. In case of death prior to an event the time of death will be taken as censoring time (or 12:00 if not available).
Length of hospital stay since hospital admission (hours) [Time-to event]	(Date and time of event or censoring - date and time of hospital admission)/3600, rounded to one decimal
Time to readiness for discharge since hospital admission (hours) [Time-to-event]	Subjects who complete or withdraw from the study prior to the event will be censored at the date of completion or withdrawal. If the time is not available they will be censored at 12:00. In case of death prior to an event the time of death will be taken as censoring time (or 12:00 if not available).
ICU duration of stay (hours) [Duration]	sum of [(end date and time of event - start date and time of event)/3600], rounded to one decimal
Duration of supplemental oxygen (hours) [Duration] (3 separate parameters: supplemental oxygen, invasive ventilator, non-invasive ventilator)	If the end date is missing, the end date is considered to be after study completion or withdrawal. If the initial start time is prior to the first dose of study drug, the duration prior to the first dose of study drug will be deducted from the overall duration.
Need for feeding, hydration by IV catheter/enteral tube (hours) [Duration] (2 separate parameters)	If the end date and time is after the study completion/discontinuation, the duration after the date and time of study completion/discontinuation will be deducted from the overall duration. If the time is not available it will be put at 12:00.
Time to end of Oxygen supplementation (hours)	(Date and time of event or censoring - date and time of first dose of

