Time to non-detectability (hours) [interval censored]	The boundaries of the censoring intervals are defined as the number of hours from the start of treatment. The left boundary of the interval is the last positive assessment before the first confirmed negative sample which is not followed by a confirmed positive sample (at baseline every subject is considered positive). If no negative samples are observed, the left boundary will be the last sample obtained. The right boundary of the interval is the first confirmed negative sample which is not followed by a confirmed positive sample. If this is not observed, the interval is right censored. A confirmed positive sample is defined as two consecutive non-negative samples; a confirmed negative sample is defined as two consecutive negative samples. Last obtained sample, whether positive or negative, is always considered confirmed.
Log viral load area under the curve from baseline to 10 days post first dose of study drug ($AUC_{0-10 \text{ days}}$).	
The $AUC_{0-10 \text{ days}}$ will be derived based on trapezoid method:
 $AUC_{0-10 \text{ days}} = AUC_{0-7 \text{ days}} + \frac{3}{2}(y_7 + y_{10})$ 
where y_7 is the log 7 viral load at day 10 and y_{10} is the log 10 viral load at day 10.
 
The following rules will be applied to deal with missing values before calculating the Viral load AUC:
 
 • If the last observations are missing, the last available observation will be carried forward. Unscheduled assessments will be included and will be eligible for

	
carrying forward until Day 10.
 
 In case multiple nasal swabs were taken on a single day the average on the log scale will be used as the value for that subject.

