Log viral load area under the curve from baseline to 14 days post first dose of study drug ($AUC_{0-14 \text{ days}}$).	
The $AUC_{0-14 \text{ days}}$ will be derived based on trapezoid method:
 $AUC_{0-14 \text{ days}} = AUC_{0-10 \text{ days}} + \frac{4}{2}(y_{10} + y_{14})$ 
where y_{10} is the log 10 viral load at day 10 and y_{14} is the log 10 viral load at day 14.
 
The following rules will be applied to deal with missing values before calculating the Viral load AUC:
 
 If the last observations are missing, the last available observation will be carried forward until Day 14. In case multiple nasal swabs were taken on a single day the average on the log scale will be used as the value for that subject.

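### SAP Table 1 adds day-width segments to an AUC0-7 defined in hours, so the derived AUC0-10 and AUC0-14 under-weight the period after Day 7 by a factor of 24; the Katz time labelled in days is computed in hours

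*SAP*

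**What the plan says.** **Viral load AUC.** SAP 4.2.3.1 gives the trapezoidal formula for AUC0-7: half the sum of (y_i + y_(i-1)) times (t_i - t_(i-1)). It states that t_i "is the time in hours post baseline". The same paragraph says the calculation is "based on planned days of sampling".

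Table 1 in SAP 4.2.4.1 extends this value in two rows:

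- "Log viral load area under the curve from baseline to 10 days post first dose of study drug": AUC0-10 = AUC0-7 + (3/2)(y7 + y10).
- "Log viral load area under the curve from baseline to 14 days post first dose of study drug": AUC0-14 = AUC0-10 + (4/2)(y10 + y14).

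Neither row has a conversion factor. The first row also describes y7 with the wrong log base (7) and the wrong day (10).

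AUC to Day 10 and to Day 14 are named secondary endpoints in protocol 2.1.2 and SAP 4.2. For testing and estimating them, SAP 4.2.4.2 refers to the repeated-measures model used for the primary endpoint.

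**Katz time to event.** The Table 1 row is headed "Time to return to pre-RSV functional status (KATZ ADL score) (days) [Time-to-event", and SAP 4.2.4.2 repeats days as the unit. The formula divides a date-time difference by 3600. The row "Length of hospital stay (hours) [Time-to event" uses the same divisor and is labelled in hours.

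**The concern.** A trapezoid sum is meaningful only if all its intervals share a unit. AUC0-7 is in log10.hours and the added segments are in log10.days, so a programmer who codes the text as it stands produces an AUC0-10 and AUC0-14 that are little more than AUC0-7. Any listing, summary or supportive analysis built on those individual values would barely register what happens between Day 7 and Day 14. The values would also not be comparable with the model-based estimates.

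For Katz, what is at stake is the reported scale: a return to pre-RSV function at 7 days would be printed as 168.0 under a heading that says days.

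**Working it through.** **1. Check the stated coefficients.** A trapezoid coefficient is half the interval width.

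| Segment | Table 1 | t in days | t in hours | Hours / Table 1 |
|---|---|---|---|---|
| Day 7 to 10 | 3/2 = 1.5 | 3/2 = 1.5 | 72/2 = 36 | 36/1.5 = 24 |
| Day 10 to 14 | 4/2 = 2 | 4/2 = 2 | 96/2 = 48 | 48/2 = 24 |

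Table 1 is reproduced exactly with t in days and not with t in hours. The factor of 24 needs no assumption about the data.

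**2. Weights in AUC0-14.** With daily samples 24 hours apart up to Day 7, y7 carries 24/2 = 12 from AUC0-7, plus its share of the next segment.

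| | y7 | y10 | y14 |
|---|---|---|---|
| As written | 12 + 1.5 = 13.5 | 1.5 + 2 = 3.5 | 2 |
| Hours throughout | 12 + 36 = 48 | 36 + 48 = 84 | 48 |

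**3. Constant load y, Day 1 as time 0.** AUC0-7 = 6 x 24 x y = 144y.

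- AUC0-10: 144y + 3y = 147y as written; 144y + 72y = 216y in hours. Share after Day 7: 2.0% against 33.3%.
- AUC0-14: 147y + 4y = 151y as written; 216y + 96y = 312y in hours. Share after Day 7: 4.6% against 53.8%.

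**4. Declining load.** This is an assumed profile, not taken from the documents: 6 log10 at Day 1, falling 0.4 log10 per day. Then y7 = 3.6, y10 = 2.4 and y14 = 0.8.

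- AUC0-7 = (6 + 3.6)/2 x 144 = 691.2 log10.h.
- As written: 691.2 + 1.5 x 6.0 + 2 x 3.2 = 691.2 + 9.0 + 6.4 = 706.6. Share after Day 7: 15.4/706.6 = 2.2%.
- In hours: 691.2 + 36 x 6.0 + 48 x 3.2 = 691.2 + 216 + 153.6 = 1,060.8. Share after Day 7: 369.6/1,060.8 = 34.8%.

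Two other assumed profiles give the same picture for AUC0-14. A decline from 6.0 to 1.0 log10 gives 2.0% against 33.0%; a slower decline from 6.0 to 2.5 gives 3.0% against 43.0%.

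**5. Where the derived values are used.**

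- The primary endpoint comes from the mixed model in SAP 4.2.3.2. Its contrast weights are 4/4 = 1 for Days 2 to 6 and 2/4 = 0.5 for Day 7, which is a day scale.
- The supportive linear model in 4.2.3.2 and the quartile analyses in 4.6 use the AUC to Day 7, which is internally consistent in hours.
- The Day 10 and Day 14 comparisons in 4.2.4.2 use the primary model, not the Table 1 values.

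**6. Katz.** SAP section 2 names SAS. Assume date-time differences in seconds, which is what makes the rows labelled in hours correct. Seven days is 7 x 86,400 = 604,800 seconds. Divided by 3600 this is 168.0; divided by 86,400 it is 7.0. The ratio is 86,400/3600 = 24.

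**The case against.** The strongest reply is that no specified test uses the faulty values. That stands: the SAP sends the Day 10 and Day 14 AUC comparisons to the mixed model, and no listed test, contrast or quartile analysis takes the individual AUC0-10 or AUC0-14 as input.

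A reader might infer that these secondary endpoints cannot show rebound or late clearance, and that this was their purpose. The documents do not support either step. They list the two AUCs without giving a rationale. Late viral load is also covered by viral load over time, time to undetectability (including an interval-censored version that takes account of later confirmed positives) and the proportion undetectable at each time point. None of these depends on the Table 1 AUC formulas.

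A second reply is that days were evidently meant, given the reference to planned sampling days, the day-scale contrast weights and the day widths in Table 1. That is plausible, and it points to the simplest correction. But the explicit definition is hours, so one place has to change in either case.

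A third reply is that the Katz and y7 slips are labelling errors. That is largely right. A constant factor of 24 leaves Kaplan-Meier ordering and accelerated failure time ratios unchanged, and a value such as 168 days would stand out in a study with about 28 days of participation. The displayed quantiles would still be wrong for their label.

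**Conclusion.** The derivation rule for the individual AUC0-10 and AUC0-14 is wrong as written. Every segment after Day 7 is under-weighted by exactly 24-fold relative to the hours definition of AUC0-7. How much this moves a total depends on the viral load profile; across the constant and declining profiles above, the share of AUC0-14 from after Day 7 falls from between 33% and 54% to between 2% and 5%.

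The effect is confined to the derived trapezoidal values and to any summary or supportive analysis that uses them. The primary endpoint is unaffected. So is the model-based inference on AUC to Day 10 and Day 14, provided the Table 1 values are not fed into it.

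The Katz medians and quartiles would be 24 times too large for a label in days, assuming date-times in seconds; the treatment comparisons for that endpoint do not change. The point is worth correcting because it concerns stated formulas for named secondary endpoints, not because it threatens the trial's main conclusions.

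**What to change.** Use one time unit for all three AUCs. The simplest change is to define t_i in days in SAP 4.2.3.1. The 3/2 and 4/2 terms then stand, and the trapezoidal values are on the same day scale as the primary model's contrast weights. Alternatively, keep hours and write AUC0-10 = AUC0-7 + 36(y7 + y10) and AUC0-14 = AUC0-10 + 48(y10 + y14).

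In the AUC0-10 row, define y7 as the log10 viral load at Day 7.

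For Katz, either divide by 86,400 and keep the label in days, or keep 3600 and relabel the endpoint in hours in both 4.2.4.1 and 4.2.4.2.

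The cost is SAP wording and the matching lines of derivation code. No data collection, sample size or test is affected.
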